### **9.2.1. Serious Adverse Events**

An SAE is any AE from this study that results in one of the following:

- death
- initial or prolonged inpatient hospitalization
- a life-threatening experience (that is, immediate risk of dying)
- persistent or significant disability/incapacity
- congenital anomaly/birth defect
- events considered significant by the investigator based upon appropriate medical judgment

Study site personnel must alert Lilly, or its designee, of any SAE within 24 hours of investigator awareness of the event via a sponsor-approved method. If alerts are issued via telephone, they are to be immediately followed with official notification on study-specific SAE forms. This 24-hour notification requirement refers to the initial SAE information and all follow-up SAE information.

Although all AEs are recorded in the CRF after signing informed consent, SAE reporting begins after the subject has signed informed consent and has received investigational product.

However, if an SAE occurs after signing informed consent, but before receiving investigational product, AND is considered reasonably possibly related to a study procedure then it MUST be reported.

Investigators are not obligated to actively seek AEs or SAEs in subjects once they have discontinued from and/or completed the study (the subject summary CRF has been completed). However, if the investigator learns of any SAE, including a death, at any time after a subject has been discharged from the study and he/she considers the event reasonably possibly related to the study treatment or study participation, the investigator must promptly notify Lilly.

#### **9.2.1.1. Suspected Unexpected Serious Adverse Reactions**

Suspected unexpected serious adverse reactions (SUSARs) are serious events that are not listed in the IB and that the investigator identifies as related to investigational product or procedure. United States 21 CFR 312.32 and European Union Clinical Trial Directive 2001/20/EC and the associated detailed guidances or national regulatory requirements in participating countries require the reporting of SUSARs. Lilly has procedures that will be followed for the recording and expedited reporting of SUSARs that are consistent with global regulations and the associated detailed guidances.

### **9.2.2. Complaint Handling**

Lilly collects product complaints on investigational products and drug delivery systems used in clinical trials in order to ensure the safety of study participants, monitor quality, and to facilitate process and product improvements.

Subjects should be instructed to contact the investigator as soon as possible if he or she has a complaint or problem with the investigational product so that the situation can be assessed.

## **9.3. Treatment of Overdose**

For the purposes of this study, an overdose of LY3185643 is considered any doses higher than the doses assigned through randomization. An overdose of rGlucagon is considered as any dose higher than 1 mg (the upper limit of the approved dosage in the prescribing information). Refer to the IB for LY3185643 and the prescribing information for rGlucagon (2012) for management of inadvertent treatment overdose.

## **9.4. Safety**

### **9.4.1. Laboratory Tests**

For each subject, laboratory tests detailed in [Appendix 2](#) should be conducted according to the Schedule of Activities (Section [2](#)).

### **9.4.2. Physical Examination**

Physical examinations and routine medical assessments will be conducted as specified in the Schedule of Activities (Section [2](#)).

### **9.4.3. Vital Signs**

For each subject, vital signs measurements should be conducted according to the Schedule of Activities (Section [2](#)).

Blood pressure and pulse rate should be measured after at least 5 minutes supine.

If orthostatic measurements are required, subjects should be supine for at least 5 minutes and stand for at least 3 minutes.

If the subject feels unable to stand, supine vital signs only will be recorded.

Additional vital signs may be measured during each study period if warranted at the discretion of the investigator.

### **9.4.4. Electrocardiograms**

For each subject, ECGs should be collected according to the Schedule of Activities (Section [2](#)).

Any clinically significant findings from ECGs that result in a diagnosis and that occur after the subject receives the first dose of the investigational product should be reported to Lilly, or its designee, as an AE via CRF.

#### **9.4.4.1. Continuous 12-Lead ECG Monitoring**

Continuous 12-lead ECG monitoring does not allow bedside printing or viewing of ECGs extracted from the signal recorded. Thus, for subject safety, ECGs must be recorded by a local, static 12-lead ECG device at the times specified in the Schedule of Activities (Section 2). These safety ECGs will not be transmitted to a central ECG laboratory. Safety ECGs must be interpreted by the investigator or qualified designee soon after the time of collection. This review will be documented and provides information for immediate subject management. If the ECG shows a clinically significant quantitative or qualitative change from baseline, the investigator or qualified designee will assess the subject for symptoms (for example, palpitations, near syncope, syncope) and determine if the subject can continue in the study. The investigator or qualified designee is responsible for subject management. If the investigator determines that the changes identified in the ECG are clinically relevant, an applicable AE should be recorded on the subject CRF.

##### ***9.4.4.1.1. Recordings for Data Analysis***

Continuous 12-lead recordings will be performed according to the Schedule of Activities (Section 2). Patients must be in a quiet atmosphere without significant external stimulation (for example, TV, internet, etc.), remain in a supine position for at least 5 to 10 minutes before the specified ECG collection times, and remain supine but awake during ECG collection and for at least 10 minutes afterward. Subjects should be encouraged to remain still, if possible, during this time.

Digital recordings of all periods of continuous ECG recordings in individual subjects will be transferred to a central ECG laboratory designated by Lilly. The ECG laboratory will perform quality control checks for the time points of interest (for example, acquisition quality for ability to measure/interpret, demographics, and study details) and extract 15 unique 10-second ECGs at the times listed in the Schedule of Activities (Section 2).

The ECG laboratory will then store the recording as well as the extracted 10-second ECGs, and a cardiologist at the central ECG laboratory will conduct a full overread (including the measurement of all intervals) on one of the replicates that was extracted. For each set of replicates, the cardiologist will determine the RR and QT intervals and heart rate on the ECGs that were not fully overread. No reports will be issued from the central ECG laboratory back to the sites for any ECGs.

All data from the overreads will be placed in a Lilly or clinical research organization (CRO) database for analytical and study report purposes.

It is recognized that the ECG interpretations by the investigator (or qualified designee) and the cardiologist at the central ECG laboratory may be different. Interpretation of the ECG by the investigator (or qualified designee) will be used for study entry and immediate subject management. Interpretations of the ECG at the central laboratory will be used for data analysis and report-writing purposes.

#### **9.4.4.2. Telemetry**

The ECG waveform and cardiac rhythm will be monitored continuously using an ECG telemetry monitor during the inpatient stay at the CRU, from the night of Day -1 to 4 hours after the last dose on Day 1, for all 3 periods. Telemetry data from Day -1 up to approximately 1 hour before dosing will be reviewed by the investigator before administration of the first dose on Day 1. Subjects will not be dosed if any exclusion criteria are observed (for example, Exclusion Criterion [14]). Any other observations, such as changes in the ECG waveform and rhythm, should be evaluated by the investigator and the decision to dose will be at the investigator's discretion. Any confirmed abnormalities/events assessed to be clinically significant by the investigator during monitoring should be recorded in the medical record and reported as a preexisting condition or AE on the AE CRF page.

#### **9.4.5. Safety Monitoring**

The Lilly clinical pharmacologist or CRP will monitor safety data throughout the course of the study.

Lilly will review SAEs within time frames mandated by company procedures. The Lilly clinical pharmacologist or CRP will consult with the functionally independent Global Patient Safety therapeutic area physician or clinical research scientist when appropriate and periodically review:

- trends in safety data
- laboratory analytes
- AEs

If a study subject experiences elevated ALT  $\geq 3$ X ULN, ALP  $\geq 2$ X ULN, or elevated total bilirubin  $\geq 2$ X ULN, clinical and laboratory monitoring should be initiated by the investigator. Details for hepatic monitoring depend upon the severity and persistence of observed laboratory test abnormalities. To ensure subject safety and compliance with regulatory guidance, the investigator is to consult with the Lilly designated CRP regarding collection of specific recommended clinical information and follow-up laboratory tests ([Appendix 4](#)).

#### **9.4.6. Immunogenicity Assessments**

At the visits and times specified in the Schedule of Activities (Section 2), blood samples for immunogenicity testing will be collected to determine antibody production against the investigational product. Justification for the lack of paired PK samples is based on the short  $t_{1/2}$  of LY3185643 (less than 1 hour) and the long delay between the dose administration and sampling times.

Additional samples may be collected if there is a possibility that an AE is immunologically mediated. Immunogenicity will be assessed by a validated assay designed to detect anti-drug antibodies in the presence of the investigational product. Antibodies may be further characterized and/or evaluated for cross-reactive binding to native glucagon and/or their ability to neutralize the activity of the investigational product.

Samples will be retained for a maximum of 15 years after the last subject visit, or for a shorter period if local regulations and Ethical Review Boards (ERBs) allow, at a facility selected by the sponsor. The duration allows the sponsor to respond to future regulatory requests related to the investigational product. Any samples remaining after 15 years will be destroyed.

## 9.5. Pharmacokinetics

At the visits and times specified in the Schedule of Activities (Section 2), venous blood samples of approximately 4 mL each will be collected to determine the plasma concentrations of LY3185643 or glucagon. Instructions for the collection and handling of blood samples will be provided by the sponsor. The actual date and time (24-hour clock time) of each sampling will be recorded.

### 9.5.1. Bioanalysis

Samples will be analyzed at a laboratory approved by the sponsor and stored at a facility designated by the sponsor.

Concentrations of LY3185643 will be assayed CCI [REDACTED]

Concentrations of glucagon will be assayed using a validated LC/MS method.

Bioanalytical samples collected to measure investigational product concentrations will be retained for a maximum of 1 year following last subject visit for the study.

## 9.6. Pharmacodynamics

At the times specified in the Schedule of Activities (Section 2), venous blood samples will be collected and used to determine the PD effects of LY3185643 or rGlucagon. Blood will be collected to evaluate blood glucose and C-peptide (both analyzed at a central laboratory designated by the sponsor).

The sample(s) will be stored for up to a maximum of 1 year after the last subject visit for the study at a facility selected by the sponsor.

### 9.6.1. Glucodynamic Samples

Blood samples (approximately 0.2 mL each) will be obtained for the measurement of glucose at the times specified in the Schedule of Activities (Section 2) using a validated method (YSI glucose analyzer) that will be readily available at the investigative site during the inpatient periods in order to provide real-time glucose measurement. Repeat samples for counter-checking of apparent spurious results may be taken where indicated. Samples will be disposed of upon confirmation of results.

## 9.7. Genetics

This section is not applicable for this study.

## **9.8. Biomarkers**

This section is not applicable for this study.

## **9.9. Health Economics**

This section is not applicable for this study.

## 10. Statistical Considerations and Data Analysis

### 10.1. Sample Size Determination

The sample size is customary for Phase 1 studies evaluating safety, PK, and/or PD parameters and is considered sufficient to evaluate the primary objective of this study.

Subjects who discontinue the study may be replaced so that at least 18 subjects complete the study. Replacement subjects will be assigned the treatment sequence of the subject that discontinued the study.

### 10.2. Populations for Analyses

#### 10.2.1. Study Participant Disposition

A detailed description of subject disposition will be provided at the end of the study.

#### 10.2.2. Study Participant Characteristics

The subject's age, sex, weight, body mass index, height, race/subrace, or other demographic characteristics will be recorded and summarized.

### 10.3. Statistical Analyses

Statistical analysis of this study will be the responsibility of Eli Lilly and Company.

PK and PD analyses will be conducted on the full analysis set. This set includes all data from all randomized subjects receiving at least 1 dose of the investigational product and with a baseline and at least 1 postbaseline measurement for each dose according to the treatment the subjects actually received. Safety analyses will be conducted for all enrolled subjects whether or not they completed all protocol requirements.

Additional exploratory analyses of the data will be conducted as deemed appropriate. Study results may be pooled with the results of other studies for population analysis purposes.

#### 10.3.1. Safety Analyses

##### 10.3.1.1. Clinical Evaluation of Safety

All investigational product and protocol procedure AEs will be listed, and if the frequency of events allows, safety data will be summarized using descriptive methodology.

The incidence of symptoms for each treatment will be presented by severity and by association with investigational product as perceived by the investigator. Symptoms reported to occur before first dose will be distinguished from those reported as new or increased in severity during the study. Each symptom will be classified by the most suitable term from the medical regulatory dictionary.

The number of investigational product-related SAEs will be reported.

### **10.3.1.2. Statistical Evaluation of Safety**

Safety parameters that will be assessed include safety laboratory parameters, vital signs, and ECG parameters. The ECG parameters that will be assessed include the ECG heart rate and the following intervals: QT, RR, PR, and QT corrected for heart rate (QTc) using Fridericia's formula (QTcF). The safety parameters will be listed and summarized using standard descriptive statistics. Any additional analyses will be detailed in the statistical analysis plan.

## **10.3.2. Pharmacokinetic Analyses**

### **10.3.2.1. Pharmacokinetic Parameter Estimation**

PK parameter estimates for LY3185643 and rGlucagon will be calculated by standard noncompartmental methods of analysis.

The primary parameters for analysis will be maximum drug concentration ( $C_{max}$ ) and area under the concentration versus time curve (AUC). Other noncompartmental parameters, such as  $t_{1/2}$ , apparent clearance, and apparent volume of distribution, may be reported. Population PK and exposure-response analyses may be performed using PK and glucose data.

### **10.3.2.2. Pharmacokinetic Statistical Inference**

PK parameters for LY3185643 and rGlucagon will be summarized for each dose group. PK parameter estimates will be evaluated to delineate effects of dose proportionality.

## **10.3.3. Pharmacodynamic Analyses**

The PD time-action and response of LY3185643 and rGlucagon will be compared to establish the relative potency between LY3185643 and rGlucagon.

### **10.3.3.1. Pharmacodynamic Parameter Estimation**

The primary PD response variables of interest include  $T_{max}$ ,  $C_{max}$ , and change from baseline to each time point, and incremental AUCs for glucose and C-peptide. A dose-proportionality parameter will also be estimated to establish the relative potency between LY3185643 and rGlucagon. Partial AUC for glucose over appropriate time intervals will be calculated using the trapezoidal rule. The AUC for each subject after each dose will also be baseline-adjusted. Baseline for each dose will be defined as the average of predose values for that dose.

### **10.3.3.2. Pharmacodynamic Statistical Inference**

PD parameters of interest may be transformed before statistical analysis if deemed necessary. Unless specified otherwise, parameters will be analyzed using a nonlinear mixed-effects model with period, treatment (LY3185643 or rGlucagon), and dose (within treatment) as fixed effects, baseline glucose as a covariate, and subject as a random effect. The use of other influencing variables as covariates will be explored as detailed in the statistical analysis plan.

A conversion factor will be defined in the model for each parameter to estimate the relative potency of LY3185643 to rGlucagon. In addition, a conversion factor will be estimated between LY3185643 and rGlucagon for multiple parameters simultaneously using a similar mixed nonlinear model approach to account for the correlation between parameters for the same subject. Model details will be discussed in the statistical analysis plan.

All PD parameters including the baseline-corrected parameters will be summarized by dose group and tabulated. Summary statistics will be provided. The individual observed and mean (by dose group) time profile of the PD measurements after dosing will be plotted.

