## Study Schedule Protocol I8Z-MC-APCA

Procedure	Screen	Periods 1, 2, 3 a			FU/ET b	Comments
	Up to Day -28	Day -1	Day 1 c	Day 2		
Continuous ECG monitoring			X			15 ECGs will be extracted from the continuous ECG recording at -5, 30, 60, 120, and 180 minutes postdose for each Day 1 dose administration.
PK samples: LY3185643 or glucagon (minutes)			0 (predose), 15 ( $\pm 2.5$ ), 30 ( $\pm 2.5$ ), 60 ( $\pm 5$ ), 120 ( $\pm 10$ ), 180 ( $\pm 10$ )			Sampling times are relative to the time of each study drug administration.
Glucose samples (minutes)			-5 ( $\pm 2.5$ ), 0 (predose), 5 ( $\pm 1$ ), 10 ( $\pm 1$ ), 15 ( $\pm 2.5$ ), 22 ( $\pm 2.5$ ), 30 ( $\pm 2.5$ ), 45 ( $\pm 5$ ), 60 ( $\pm 5$ ), 75 ( $\pm 5$ ), 90 ( $\pm 5$ ), 105 ( $\pm 5$ ), 120 ( $\pm 5$ ), 150 ( $\pm 5$ ), 180 ( $\pm 5$ )			Blood concentrations using YSI glucose analyzer. Sampling times are relative to the time of each study drug administration.
PD samples: C-peptide, glucose (minutes)			-5 ( $\pm 2.5$ ), 0 (predose), 5 ( $\pm 1$ ), 15 ( $\pm 2.5$ ), 30 ( $\pm 2.5$ ), 60 ( $\pm 5$ ), 120 ( $\pm 5$ )			Sampling times are relative to the time of each study drug administration.
Immunogenicity (LY3195643 antibodies) samples			Any time before the first dose		X	Period 1 and Period 3 only. Prior to the first dose only.

Abbreviations: AE = adverse event; CRU = clinical research unit; ECG = electrocardiogram; ET = early termination; FU = follow-up; PD = pharmacodynamics; PK = pharmacokinetics.

Note: The site should schedule activities as appropriate. In cases where several study procedures are scheduled at the same time, the order of priority for these procedures will be as follows: PK samples, PD samples, vital signs, ECG, clinical laboratory samples.

a Each treatment period will consist of 3 days (Days -1 to 2). Subjects should return for the next period with a minimum of 3 days between treatment periods.

b FU/ET visit will occur at least 30 days after completing the last dose of study treatment.

c Study drug will be administered 3 times on Day 1 in each period. Day 1 activities will be performed 3 times on Day 1 with the sampling times corresponding to each study drug administration.

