**Table APCA.4.1. Objectives and Endpoints**

Primary Objective	Endpoints
The primary objective of this study is to evaluate the PK and PD profiles of LY3185643 and rGlucagon after single doses of study treatment	$C_{max}$ , AUC, and terminal half-life of LY3185643 and rGlucagon $C_{max}$ and AUC (change from predose) of blood glucose and C-peptide
Secondary Objective	Endpoints
To evaluate the safety and tolerability of LY3185643 after single doses of study treatment	Adverse events
Exploratory Objective	Endpoints
To evaluate immunogenicity of LY3185643 after multiple single doses of study treatment	Anti-LY3185643 antibodies

Abbreviations: AUC = area under the concentration versus time curve;  $C_{max}$  = maximum concentration;

PD = pharmacodynamic; PK = pharmacokinetic; rGlucagon = recombinant glucagon.

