9.4 Pharmacodynamic Assessment

9.4.1 Pharmacodynamic Analysis

The PD time-action and response of LY3185643 and rGlucagon will be compared to establish the relative potency between LY3185643 and rGlucagon.

The primary PD response variables of interest include t_{max} , C_{max} , change from baseline in C_{max} and change from baseline to each time point, and incremental AUCs for glucose measured by YSI glucose analyzer and C-peptide. Similar PD response variables using laboratory measured glucose will also be estimated.

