9.4.2 Pharmacodynamic Statistical Methodology

All PD parameters including the baseline-corrected parameters will be summarized by dose group and tabulated. The individual observed and mean (by dose group) time profile of the PD measurements after dosing will be plotted.

For these parameters, a linear model will be fitted to account for the PD difference between LY3185643 and rGlucagon. The model is detailed below. In addition, partial AUC for glucose over appropriate time intervals will be calculated using the trapezoidal rule. The AUC for each subject after each dose will also be baseline-adjusted. Baseline for each dose will be defined as the average of predose values for that dose.

For each PD parameter, the linear model that is proposed to account for differences between LY3185643 and rGlucagon is:

$$Y_{kl} = \beta_0 + \beta_1 d_{kl} + \beta_2 d_{kl} * Z_{kl} + u_k + e_{kl} \quad (1)$$

where k denotes the subject index, l denotes the period index, d_{kl} is the dose in mg during each period, Z_{kl} is the treatment indicator (0 for rGlucagon and 1 for LY3185643), $u_k \sim NI(0, \sigma_{u^2})$ denotes the between subject error, and $e_{kl} \sim NI(0, \sigma_{e^2})$ denotes the within-subject error. The

notation “NI” means “Normally Independent.” There is no term for the treatment group indicator Z_{kl} because at dose = 0 the response should be the same for both treatment groups. Setting the mean responses for each treatment equal to each other, it follows that:

$$\beta_0 + \beta_1 D_1 + \beta_2 D_1 = \beta_0 + \beta_1 D_0$$

where D_0 denotes the rGlucagon dose and D_1 denotes the LY3185643 dose. It follows that $D_1 = \lambda D_0$ where $\lambda = \beta_1/(\beta_1 + \beta_2)$ is the conversion factor that determines how many mg of LY3185643 are equivalent to one mg of rGlucagon. The model (1) can be reparameterized as a nonlinear mixed model:

$$Y_{kl} = \beta_0 + \beta_1 d_{kl} + (1 - \lambda)/\lambda \beta_1 d_{kl} * Z_{kl} + u_k + e_{kl}.$$

Then, the conversion factor λ (the point estimate and the 90% confidence interval) will be directly estimated from this nonlinear model. This model may be extended to allow for multiple parameter values, if deemed appropriate.

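### C-peptide parameters are corrected for their own baseline by subtraction at most (raw Cmax not at all), and neither model has a baseline C-peptide covariate, which may cost precision in the C-peptide conversion factor

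*Protocol*

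**What the plan says.** **Endpoints.** Table APCA.4.1 of the protocol places Cmax "and AUC (change from predose) of blood glucose and C-peptide" under the primary objective. Protocol 10.3.3.1 lists Tmax, Cmax, "and change from baseline to each time point, and incremental AUCs for glucose and C-peptide", and adds: "The AUC for each subject after each dose will also be baseline-adjusted". SAP 9.4.1 lists tmax, raw Cmax, the change from baseline in Cmax, the change at each time point, and "incremental AUCs for glucose measured by YSI glucose analyzer and C-peptide". It plans similar variables for laboratory glucose.

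**Baseline.** The Schedule of Activities has C-peptide drawn at -5 and 0 minutes before each dose. SAP 9.4.2 states: "Baseline for each dose will be defined as the average of predose values for that dose". SAP 9.4.3 applies the same baseline to C-peptide changes and partial AUCs.

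**Models.** Protocol 10.3.3.2 gives a default model for the PD parameters with "baseline glucose as a covariate, and subject as a random effect", makes no exception for C-peptide, and continues: "The use of other influencing variables as covariates will be explored as detailed in the statistical analysis plan". The SAP names no such variable. Its model in 9.4.2, proposed for every PD parameter, contains dose, dose by treatment and a random subject intercept. It yields the conversion factor λ with a 90% confidence interval. SAP section 3 says the SAP supersedes the protocol's statistical considerations.

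**The concern.** λ is how the plan expresses relative potency, and protocol 3.1 says relative potency will direct changes to the control algorithms. For C-peptide outcomes, the one baseline covariate that the protocol names belongs to a different analyte, and the operative SAP model has none. Restoring baseline glucose to the SAP model would still leave baseline C-peptide out.

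The random subject intercept absorbs stable differences between subjects. It does not absorb dose-to-dose variation in starting C-peptide within a subject. Such variation is plausible here: three doses are given about 4 hours apart during one fast. Protocol 5.4 expects drug concentrations and glycemia to have settled by 4 hours but says nothing about C-peptide, whose sampling stops at 120 minutes. In raw Cmax this variation stays in the residual. In the subtracted parameters it enters with a coefficient fixed at -1, whether or not that suits the data. At stake is the width of the interval for λ.

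**Working it through.** **Data available.** C-peptide has 7 draws per dose (-5, 0, 5, 15, 30, 60 and 120 minutes). 7 × 9 doses = 63 samples, which matches Appendix 5. Of these, 2 × 9 = 18 are predose.

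**Plan's own figure.** There is none to reproduce. Protocol 10.1 and SAP 7 give no power, effect size or SD.

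**Assumed inputs.** Let ρ be the within-subject correlation between baseline and post-dose C-peptide, and k the within-subject baseline SD divided by the post-dose SD. Neither is in the documents. I use ρ = 0.3, 0.5 and 0.7, and k = 1 and 0.5.

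**Formulas.** Relative to the residual variance of the raw parameter:

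- raw: 1
- change from baseline: 1 + k² − 2ρk
- baseline as covariate: 1 − ρ²

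Because λ = β1/(β1 + β2), its delta-method SE scales with the residual SD. The interval with the covariate, relative to the interval without it, is therefore:

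- raw Cmax: √(1 − ρ²)
- change parameters: √[(1 − ρ²)/(1 + k² − 2ρk)], which is √[(1 + ρ)/2] when k = 1

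| ρ | Raw Cmax | Change, k = 1 | Change, k = 0.5 |
|---|---|---|---|
| 0.3 | √0.91 = 0.954 (5% narrower) | √0.65 = 0.806 (19%) | √(0.91/0.95) = 0.979 (2%) |
| 0.5 | √0.75 = 0.866 (13%) | √0.75 = 0.866 (13%) | √(0.75/0.75) = 1 (0%) |
| 0.7 | √0.51 = 0.714 (29%) | √0.85 = 0.922 (8%) | √(0.51/0.55) = 0.963 (4%) |

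The change-score variance minus the covariate variance is (1 + k² − 2ρk) − (1 − ρ²) = (k − ρ)², which is never negative. Apart from the degrees of freedom spent, the covariate cannot do worse than subtraction, and it gains nothing when k = ρ. Against the raw parameter, the variance gain is ρ².

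**Simulation check.** The set-up was 18 subjects on the nine doses of Table APCA.5.1, a linear dose response, true λ = 1, k = 1, subject effects fitted as fixed, and 1,500 runs per setting. The ratio of the SD of λ without the covariate to the SD with it was:

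| ρ | Raw, simulated | Raw, formula | Change, simulated | Change, formula |
|---|---|---|---|---|
| 0.3 | 1.03–1.04 | 1.05 | 1.23–1.28 | 1.24 |
| 0.5 | 1.15 | 1.15 | 1.14–1.16 | 1.15 |
| 0.7 | 1.37–1.41 | 1.40 | 1.06–1.09 | 1.08 |

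Across all settings, including ρ = 0.9, mean λ lay between 0.999 and 1.007 for the raw, change and covariate analyses. The effect is on precision, not bias.

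**The case against.** The strongest reply is that C-peptide is already baseline-corrected. A reader who sees only the model statements might infer that these endpoints are never adjusted for baseline C-peptide. The documents do not support that: the change from predose, the incremental AUC and the baseline-adjusted AUC all subtract the C-peptide predose mean. Only raw Cmax (and Tmax) is left uncorrected, and the SAP also analyses the change from baseline in Cmax. For most parameters the issue is therefore a change score against a covariate, and both are valid. This part of the reply stands.

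Several other points against a stronger reading also stand:

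- **Size.** The larger gains for change parameters need roughly equal baseline and post-dose SDs. At k = 0.5 they nearly vanish.
- **Power.** A reader might turn the narrower interval into a gain in power to exclude λ = 1. The plan has no such test and states no power, so no power figure applies.
- **Imbalance.** A reader might suspect uncorrected imbalance between treatments at the influential high doses. Every completer receives all nine doses, and the simulation shows no bias.
- **Model form.** The simulation fits subject effects as fixed, whereas the SAP uses a random intercept. A single uncentred baseline term in that model would mix between-subject and within-subject associations, so the covariate has to be entered with care.

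It can also be said that the protocol leaves further covariates to the SAP. That would answer the point if the SAP had named one. It does not.

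**Conclusion.** The point holds as a matter of precision. C-peptide parameters are corrected for their own baseline by subtraction or not at all, and neither model carries baseline C-peptide, although two predose values exist for every dose. The 90% interval for the C-peptide λ may be wider than necessary. The narrowing available is about 5% to 29% for raw Cmax over ρ = 0.3 to 0.7. For change parameters it runs from 19% down to 8% if the SDs are equal, and is 0% to 4% if the baseline SD is half the post-dose SD. The simulation check also assumes a linear dose response and true λ = 1.

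The estimate of λ is not invalid. The reason to act is that ρ and k are unknown in advance and the covariate is the choice that does not depend on guessing them. It loses only a degree of freedom or two out of about 18 × 9 = 162 profiles, and the protocol already accepts a baseline covariate in this model. The SAP's omission of the protocol's glucose covariate, while its section 11 reports no changes, is a related but separate discrepancy.

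**What to change.** In protocol 10.3.3.2 and SAP 9.4.2, state that each PD parameter, raw or change from baseline, is adjusted for the per-dose baseline of the same analyte, using the average of predose values already defined:

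- YSI glucose baseline for YSI glucose parameters
- laboratory glucose baseline for laboratory glucose parameters
- C-peptide baseline for C-peptide parameters

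Enter the baseline as two terms, the subject's mean baseline and the deviation of each dose's baseline from that mean. The random-intercept model then keeps the between-subject and within-subject associations apart. With these terms in the model, raw Cmax and change from baseline in Cmax give the same λ, because subtracting the baseline only shifts its coefficients by 1.

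The cost is a wording change in both documents and one or two degrees of freedom per model. No new samples or visits are needed.
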